#### 2. STUDY DESIGN

Study ALN-AS1-002 is an open-label, extension study designed to evaluate the long-term safety, clinical activity of givosiran in patients with AIP. The number of patients included up to 16 patients from Part C in the parent study ALN-AS1-001.

Eligible patients who completed Part C in the parent study either received the same dosing regimen as the pivotal Phase 3 study (e.g. 2.5 mg/kg every month) or had 1 or more dosing regimen changes across studies. The change in dosing regimen for a patient may occur due to emerging data and decisions from the Safety Review Committee (SRC). After a patient has completed 12 months of givosiran administration in this study (6 months in an every month dosing regimen), and where applicable country and local regulations and infrastructure allow, study procedures, including givosiran administration may take place at the patient's home by a healthcare professional. The expected duration of treatment for each patient is up to 36 months (3 years) followed by a post-treatment visits at either month 39/Early Termination visit or month 42.

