### 6.4. Study Groups

All tables and figures will be presented by the following study groups:

- Randomized treatment arm in the parent study/Current treatment arm (i.e., column for givosiran/givosiran vs. placebo/givosiran)
- Total (pooling regardless of randomized treatment arm in the parent study)

Summaries of key efficacy (e.g. PD and Clinical Activity) will also include study group:

• Intended Dose Group (i.e., givosiran 2.5 mg/kg monthly in ALN-AS1-002)

The following rules will be used:

- In analyses on PD measurements using the Intended Dose group, summaries at each postbaseline visit will be based on patients who are on 2.5 mg/kg at that visit.
- In analyses on clinical activity assessments (porphyria attacks and hemin use using the Intended Dose group, only events that occur between the first day of dosing and the last day of dosing with the intended dose regimen (2.5 mg/kg once monthly) are included.

An intended dose period will be defined as starting from the first dose of 2.5mg/kg Givosiran monthly.

Summaries of key safety (e.g. AEs) will also include study groups based upon initial dose in ALN-AS1-002:

- Initial dose of 2.5 mg/kg (monthly)
- Initial dose of 5 mg/kg (at any frequency)

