### 7.5.2. Clinical Activity

Clinical activity of ALN-AS1 will be assessed by the number of porphyria attacks and by the number of doses of hemin administered.

Analysis of Clinical Activity will be performed on the Safety Analysis Set.

**Porphyria attacks:** An attack will be defined as any event with preferred term="Porphyria" recorded on Adverse Event eCRF. Attacks which occur within the same date (i.e., end date of attack is the same date as start date of the next attack) will be counted as one attack. When collapsing attacks that occurred on the same date, the following rules will be applied for severity and location:

- 1. Severity will be assigned the maximum severity among the records.
- 2. Location will be assigned 'hospital' if  $\geq 1$  attack with location=hospital. Location will be assigned 'outpatient' if  $\geq 1$  attack with location=outpatient Location will be assigned 'home' if all the records state location=home. Location will be assigned 'other' if all the records state location=other.

The number of porphyria attacks during the treatment period (attacks with start dates on or after date of first dose) will be summarized. Annualized attack rate (AAR) per patient will be calculated as the total number of porphyria attacks divided by the total person-days at risk and multiplied by the total number of days in a year (365.25). Person-days at risk will be defined as: (date patient went off study – date of first dose+1). For an interim snapshot, the person-days will be defined by date of the first dose until the minimum of the date of the interim snapshot cut-off date or date the patient went off study. For calculation of AAR, only records with non-missing start and stop dates will be considered.

Porphyria attacks will be summarized separately in each subgroup:

- 1. Composite attacks: Attacks requiring hospitalization, urgent health care (i.e. outpatient clinic, Emergency Department, etc.) or IV hematin at home.
- 2. Attacks requiring hospitalization
- 3. Attacks requiring urgent health care (i.e. Outpatient)
- 4. Attacks required treatment with IV hematin at home
- 5. Attacks not treated with IV hematin at home
- 6. All attacks

For each subgroup, the total number of events, total person-years (total days/365.25), mean rate (total number of events/total person-years) and SEM will be presented for each study group. The

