SEM will be calculated using Cochran's estimate of SEM for weighted mean [1]. Attacks for each subgroup will display the rates separately for each phase of study: run-in (ALN-AS1-001 study) and treatment phase (ALN-AS1-002). A tabular summary of percentage change (%) in AAR rate from run-in to treatment phase will be also calculated per cohort. In addition, a by-patient listing will summarize the porphyria attacks in each of the subgroups. An exploratory analysis of AAR based on 6 months of givosiran dosing and beyond 6 months may be explored.

In addition, clinical activity will be assessed by duration and severity of attack (mild/moderate/severe). Reduction from run-in period (ALN-AS1-001 study) in composite to all attacks ratios will be assessed.

Hemin: Dosing with hemin will be summarized for doses during the treatment period (hemin start dates on or after the first dose of givosiran in this study). Hemin dosing will be identified as medication with standardized medication terms such as 'hematin', 'haem arginate' or 'hemin'. Annualized rate of hemin dosing will be summarized in the same manner as porphyria attacks (i.e., mean rate, SEM, person-years, total events). For the calculation of annualized rate of hemin, only records with non-missing start and stop dates will be considered. These summaries will also be presented in the same manner (i.e. separately for each cohort displaying results from each phase of study: run-in (ALN-AS1-001 study) and treatment phase (ALN-AS1-002). An exploratory analysis of Annualized rate of hemin dosing based on 6 months of givosiran dosing and beyond 6 months may be explored.

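### The SEM prescribed for attack and hemin rates is exactly 0 in any cell with no events and undefined with one patient, and the SAP has no rule for those cells

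*SAP*

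**What the plan says.** SAP section 7.5.2 pools events over person-time within each cell: "mean rate (total number of events/total person-years) and SEM will be presented for each study group". It then fixes the estimator: "SEM will be calculated using Cochran's estimate of SEM for weighted mean [1".

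The cells are numerous. "Porphyria attacks will be summarized separately in each subgroup", and six attack categories follow. By phase, "Attacks for each subgroup will display the rates separately for each phase of study: run-in (ALN-AS1-001 study) and treatment phase (ALN-AS1-002". Hemin is treated alike: "Annualized rate of hemin dosing will be summarized in the same manner as porphyria attacks (i.e., mean rate, SEM, person-years, total events".

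The patients are few. SAP section 2 states: "The number of patients included up to 16 patients from Part C in the parent study ALN-AS1-001". Section 6.4 splits them by "Randomized treatment arm in the parent study/Current treatment arm (i.e., column for givosiran/givosiran vs. placebo/givosiran", adds a Total column, and adds an intended-dose group for the clinical activity summaries. Section 6.6 adds interim cuts.

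Section 7.5.2 gives no rule for the SEM when a cell has no events, only one patient, or identical rates in all patients. It plans no confidence interval for these rates; the term appears only in the abbreviation list.

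**The concern.** An SEM is printed to tell the reader how precisely a rate is known. One computed from differences between patients cannot do this when there are none, and that happens most readily where information is thinnest: a rare attack category, few patients, short follow-up. A rate of 0.00 with an SEM of 0.00 then looks more precise than a neighbouring cell with one attack, although the two rest on almost the same evidence.

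The cells most exposed are the rarer categories, such as attacks treated with IV hematin at home, in the smaller parent-arm column, the intended-dose group, the run-in phase or an early interim cut. Section 6.6 says that interim outputs serve regulatory work and publications, so these tables may be read outside the study team.

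**Working it through.** **Inputs from the SAP.** At most 16 patients (section 2). Two parent-arm columns plus Total (section 6.4), so the smaller arm column has at most 16/2 = 8. Treatment up to 3 years (section 2). Six attack categories plus hemin, in two phases (section 7.5.2): 7 rates × 3 columns × 2 phases = 42 cells before the intended-dose group and interim cuts.

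**Assumptions.** The SAP does not give column sizes, run-in length, interim dates or category-specific rates. It names the estimator by citation and does not print it, so the usual form is used. No SEM value is stated in the plan, so there is nothing to reproduce.

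**Step 1: the formula.** For patient i let P_i be person-time, E_i events and X_i = E_i/P_i. The pooled rate R = ΣE_i/ΣP_i is the mean of the X_i weighted by P_i, so the weights are person-time. With P̄ the mean person-time,

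SEM² = n/[(n−1)(ΣP)²] × {Σ(P_iX_i − P̄R)² − 2R Σ(P_i − P̄)(P_iX_i − P̄R) + R² Σ(P_i − P̄)²}.

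The bracket is the sum of squares of (P_iX_i − P̄R) − R(P_i − P̄) = E_i − R·P_i. Hence

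SEM² = n/[(n−1)(ΣP)²] × Σ(E_i − R·P_i)².

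**Step 2: the degenerate cells.**
- No events, n ≥ 2: every E_i = 0 and R = 0, so each term is 0 and SEM = 0. Numerical evaluation gave 0 for 16 patients with equal follow-up and for 4 patients with equal and with unequal follow-up.
- Equal rates: 4 patients with 1 attack each in 1 year give R = 4/4 = 1.0, each E_i − R·P_i = 0, and SEM = 0.
- One patient: the factor n/(n−1) divides by 0, so the SEM is undefined.

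**Step 3: contrast with one event.** Take 4 patients with 1 year each and a single attack. R = 1/4 = 0.25. The residuals are 0.75 once and −0.25 three times, so the sum of squares is 0.5625 + 3 × 0.0625 = 0.75. SEM² = 4/(3 × 16) × 0.75 = 0.0625, and SEM = 0.25. Remove that one attack and the printed SEM falls from 0.25 to 0.

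**Step 4: what zero events allow.** The exact two-sided 95% Poisson upper limit U solves exp(−U × PY) = 0.025, so U = 3.689/PY. The last column shows how often a zero-event cell would arise at an assumed true rate of 0.1 per year, exp(−0.1 × PY).

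| Person-years | Example (assumed) | Printed SEM | Upper limit per year | P(no events) at 0.1/year |
|---|---|---|---|---|
| 4 | 4 patients × 1 year, or 16 × 0.25 | 0 | 0.92 | 67% |
| 12 | 4 patients × 3 years | 0 | 0.31 | 30% |
| 48 | 16 patients × 3 years | 0 | 0.08 | 1% |

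**The case against.** The strongest reply is that nothing depends on this SEM. Section 6.1 makes all summaries descriptive, section 6.6 excludes hypothesis tests at interim, and 7.5.2 forms no interval from the SEM and plans no error-bar plot of attack or hemin rates. Total events and person-years are printed beside it, so a reader who sees zero events in a stated person-time can derive the limit. Section 1 places the table shells in a separate document, which may already handle such cells. All of this stands. It limits the point to presentation, but it does not make 0 a correct standard error, and 7.5.2 is where the rule belongs.

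The size of the problem also depends on quantities that the SAP does not give. For the Total column at full follow-up the upper limit is only 0.08 per year and a zero-event cell is improbable at the assumed rate.

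Two stronger readings are tempting, and the documents support neither. A reader might infer that a zero SEM amounts to claiming that such attacks do not occur; the counts and person-years alongside prevent that. A reader might also infer that the SEM is materially too small in small groups even when events occur, because rate ± 1.96 SEM covers poorly there. The plan makes no such interval. In simulation with 4 patients (rates 0.5 and 3 per year, follow-up 3 years or uniform on 0.5 to 3, Poisson or gamma-Poisson counts), the root-mean-square SEM was 0.95 to 1.01 times the true standard deviation, so the variance estimate is close to unbiased. The plain average of the SEM is lower (0.76 to 0.93), largely because it is the square root of a variable, skewed variance estimate. At a low rate of 0.1 per year, nearly all the shortfall in coverage comes from the zero-event cells: among 4-patient groups with at least one event, coverage was 98% to 99%.

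**Conclusion.** The point holds as a minor error in how precision is reported. By algebra, the prescribed SEM is 0 in every zero-event cell with two or more patients, 0 when all patients have the same rate, and undefined with one patient; section 7.5.2 has no rule for any of these. That part needs no assumption beyond the usual form of the named estimator, and would hold for any SEM built only from between-patient deviations.

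The practical size does rest on assumed cell sizes. A printed SEM of 0 is compatible with rates up to 0.92 per year at 4 person-years, but only 0.08 at 48. The point therefore bears on the rarer categories in the smaller parent-arm, intended-dose, run-in and interim cells, and hardly on the final Total column. No test, interval or decision changes.

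**What to change.** Add to section 7.5.2, for attacks and hemin alike:
- The SEM is reported as not estimable when a cell has zero events, only one patient, or no between-patient variation in rate.
- Zero-event cells carry an exact two-sided 95% Poisson upper limit, 3.689 divided by total person-years.
- A footnote states that this limit is a minimum, because it ignores variation between patients and the clustering of hemin doses.

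Make the table shells agree. The cost is a sentence or two, a footnote and a small programming change; no new data are needed. Zero-event cells will look less favourable than they do with an SEM of 0. The SEM in other cells can stay as planned.

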### 7.6. Exploratory Analyses

### 7.6.1. Characterize the PK profile of ALN-AS1

Non-compartmental analysis (NCA) for PK will be summarized in this analysis plan. For all the PK analyses, the PK Analyses Set will be used.

Plasma concentration-time data for givosiran and its metabolite, 3'(N-1) givosiran (if analyzed) will be summarized using descriptive statistics (n, mean, SD, median, quartiles, minimum, maximum and %CV). Concentrations will be summarized by scheduled study visit and time collection (e.g.  $C_{p, 2h}$ ,  $C_{p, 6h}$ , etc.). Other pharmacokinetic parameters will not be determined due to the sparse PK sampling in the study.

Antidrug antibody (ADA): Results will be presented in a listing. For each patient, the collection of ADA screening status, confirmatory status and titer value (if applicable) will be displayed at each visit. A tabular summary of ADA titer values may also be generated.

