### 7.4. Safety Analyses

The primary objective of this study is to evaluate the long-term safety and tolerability of givosiran in patients with AIP. All analyses will use the Safety Analysis Set. All clinical safety

laboratory data collected from the central laboratory will be used to evaluate safety. For summaries of ECG data, these will be performed separately based upon data collected locally and centrally.

**Parameters:** Safety and tolerability assessments for givosiran will include study drug exposure, AEs, clinical laboratory parameters (hematology, serum chemistry, liver function test [LFT], urinalysis, coagulation), vital signs, 12-lead ECGs, concomitant medication, and physical examinations.

**Exposure:** Summaries will include descriptive statistics of the duration of treatment (days) and total number of doses received. Additional summaries of the cumulative number of patients (percentage) that completed study treatment intervals (e.g.  $\ge 1$  day,  $\ge 1$  month,  $\ge 3$  month, etc.) and the number of patients (percentage) that completed study treatment at the latest visit interval will also be displayed. Additionally, cumulative number of doses received at home will be displayed.

The date of the last exposure to study drug is defined as the earliest day of the following dates:

- Last dose date + 27 days
- Analysis cut-off date
- The date of EOS

Duration of exposure (days) is defined as date of the last exposure – date of the first dose +1. Dose interruptions and compliance will not be considered when calculating of duration of exposure.

A separate per-patient exposure listing will be generated to display the dosing regimen in the parent study (ALN-AS1-001) and actual dosing (mg/kg) regimen(s) in this study.

**Adverse Events:** AEs will be coded using the MedDRA coding system (version 21.0 or later) and displayed in tables and data listing by SOC and PT. Patients who report multiple occurrences of the same PT will be classified according to the most related or most severe category. Patients with a missing severity or missing relationship to study drug will be classified to the most related or most severe category.

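### Plasma concentrations are summarised with no dose stratum, so at any visit where 2.5 mg/kg and 5 mg/kg patients are both sampled the mean, SD and %CV mix doses

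*SAP*

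**What the plan says.** Section 7.6.1 gives descriptive statistics, including %CV, for givosiran and, if analysed, its metabolite. On strata it says only: "Concentrations will be summarized by scheduled study visit and time collection". It names no dose stratum, dose normalisation or restriction to one dose. It also says that no other PK parameters will be derived because sampling is sparse, so this is the only PK summary in the SAP.

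The columns come from section 6.4: "All tables and figures will be presented by the following study groups". The groups are parent-study arm with current arm, and "Total (pooling regardless of randomized treatment arm in the parent study".

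Section 6.4 then adds dose-based groups for two kinds of output:
- For efficacy: "Summaries of key efficacy (e.g. PD and Clinical Activity) will also include study group", meaning the Intended Dose Group at 2.5 mg/kg monthly. For PD in that group, "summaries at each postbaseline visit will be based on patients who are on 2.5 mg/kg at that visit".
- For key safety, with AEs as the example: groups by starting dose in this study, 2.5 mg/kg monthly or "Initial dose of 5 mg/kg (at any frequency").

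Section 2 says that some patients "had 1 or more dosing regimen changes across studies". Section 7.4 plans a per-patient exposure listing that includes "actual dosing (mg/kg) regimen(s) in this study".

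**The concern.** A plasma concentration can be interpreted only against the dose that produced it. The SAP recognises more than one dose level in this study and allows regimens to change. It applies an on-dose-at-that-visit rule to PD in the Intended Dose Group. Concentration depends on dose more directly than PD does, yet the concentration tables have no such rule.

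Two misreadings become possible. If patients move between doses during the study, the mean concentration can shift from visit to visit with no change in pharmacokinetics, and this could be taken for a time or accumulation effect. If the two arm columns hold different shares of 5 mg/kg patients, a gap between givosiran/givosiran and placebo/givosiran could be taken for an effect of earlier exposure. Mixing doses also changes the SD and %CV, so the reported variability no longer describes either dose.

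**Working it through.** The SAP states no figure on this point, so there is nothing to reproduce. The check has two parts.

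**1. Which groupings reach the PK table**

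| Output | Arm and Total | 2.5 mg/kg group | Starting-dose groups |
|---|---|---|---|
| PD, clinical activity | yes (6.4) | yes (6.4) | not named |
| AEs | yes (6.4) | not named | yes (6.4) |
| Plasma concentration | yes (6.4) | not named | not named |

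Section 7.6.1 adds visit and time point as strata, and nothing on dose. Samples at 2.5 mg/kg and 5 mg/kg from the same visit, time point and arm therefore share a cell, and all of them share the Total column.

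**2. How much mixing could matter (illustration)**

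Input from the SAP: two dose levels, 2.5 and 5 mg/kg, a ratio of 2.

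Assumptions that are not in the SAP:
- Concentration is proportional to dose.
- The within-dose CV c is the same at both doses: 40%, with 30% and 50% as a range.
- The share p of sampled patients on 5 mg/kg is 25%, 50% or 75%.

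Set the 2.5 mg/kg mean to 1, so the 5 mg/kg mean is 2. Then

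- pooled mean = (1 − p)·1 + p·2 = 1 + p
- pooled variance = (1 − p)·c² + p·(2c)² + p(1 − p)·(2 − 1)²
- pooled CV = √variance / mean

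With c = 0.40, so that c² = 0.16 and (2c)² = 0.64:

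- p = 0.25: mean 1.25; variance 0.12 + 0.16 + 0.1875 = 0.4675; CV 0.684/1.25 = 54.7%
- p = 0.50: mean 1.50; variance 0.08 + 0.32 + 0.25 = 0.65; CV 0.806/1.50 = 53.7%
- p = 0.75: mean 1.75; variance 0.04 + 0.48 + 0.1875 = 0.7075; CV 0.841/1.75 = 48.1%

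For other within-dose CVs, at the same three values of p, the pooled CV is

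- c = 30%: 47.0%, 45.9%, 39.6%
- c = 50%: 63.2%, 62.4%, 57.1%

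The pooled means do not depend on c. Measured against the 5 mg/kg mean, they are 38%, 25% and 12.5% too low.

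Two further scenarios, also assumed, show how dose mix can imitate an effect:
- Half of the patients are on 5 mg/kg at an early visit and none at a later one: the visit mean goes from 1.5 to 1.0, and 1.0/1.5 − 1 = −33%.
- One arm column has 25% on 5 mg/kg and the other 75%: the ratio of column means is 1.75/1.25 = 1.4.

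At p = 0 or p = 1 there is no distortion. Summarised within dose, the means are 1 and 2, each with CV c.

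**The case against.** The strongest reply is that the information is not lost. Section 6.1 promises by-patient data listings with study day, and section 7.4 lists each patient's actual mg/kg regimens. With up to 16 patients (section 2), a reader can match each concentration to a dose by hand. This stands. One might infer that the PK profile cannot be read at any dose, but the SAP does not support that. The problem lies in the summary statistics, and only where doses are mixed.

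Second, the SAP does not give the number of patients on each dose at any visit, the PK sampling visits, the timing of regimen changes, or how starting dose relates to parent-study arm. This also stands. A reader should not conclude that every printed mean mixes doses, or that parent arm is known to be unrelated to dose. Where all sampled patients share one dose, the summary is sound.

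Third, section 7.6.1 does not forbid further grouping, the table shells are in a separate document, and population PK is deferred to another one (section 1). This carries less weight. The SAP sets the column rule for all tables and names the exceptions, and PK is not among them. Unseen shells cannot be relied on to correct that rule.

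Fourth, PK is an exploratory objective, all summaries are descriptive, and sampling is sparse. That limits the consequence but does not make a dose-mixed mean informative.

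Finally, splitting so few patients by dose, frequency, visit and time point may leave cells too small for an SD or %CV. That is fair, and the fix allows for it.

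**Conclusion.** The point holds for the planned concentration tables. Under sections 6.4 and 7.6.1 together, these have no dose stratum, and at any visit where both dose levels are sampled the mean, SD and %CV combine them. Changes over visits and differences between arm columns may then be due to dose mix. This is more than missing detail, because the stated column rule itself produces the mixing, and the SAP already handles the same issue for PD.

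The actual size cannot be derived from the SAP. The illustrated range, a pooled mean 1.25 to 1.75 times the 2.5 mg/kg mean and a pooled CV of 48% to 55% instead of 40%, rests on dose proportionality, an assumed within-dose CV and assumed dose shares. It shows what mixing could do, not what it does in this trial. No primary or secondary conclusion depends on these tables. The change is worth making because it is cheap and because this is the only PK summary in the SAP.

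**What to change.** In section 7.6.1, state that concentrations are summarised by the actual dose (mg/kg) and regimen received at the dosing occasion to which the sample belongs, within visit and time point, with n shown in each cell. Keep the frequencies at 5 mg/kg apart.

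Where cells are too small for summary statistics, list the individual values with dose. At the least, add to the PK tables the group of patients on 2.5 mg/kg at that visit, which section 6.4 already uses for PD.

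The arm and Total columns may stay if they are shown within dose or labelled as mixing doses.

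The cost is a few lines of SAP text and one grouping variable, taken from dosing data already needed for the exposure listing in section 7.4. The downside is fewer patients per cell. This changes reporting only; it does not touch dosing.
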